4.2. Discussion of Study Design, Including the Choice of Control Groups

This study uses a factorial, placebo concurrent control design to assess the safety and immunogenicity of varying doses of the same vaccine with or without the ALFQ adjuvant. This is a Phase I study with a primary objective of characterizing the safety of the study vaccination, so saline placebo was chosen as the control.

4.3. Selection of Study Population

The study population will consist of approximately 80 healthy, HIV-uninfected, adult, RV306 recipients who were randomized to receive active vaccine. All study participants must meet the eligibility criteria enumerated in the protocol (protocol version 5.0, sections 8.4, 8.5).

4.4.2. Allocation of Participants to Study Arms (Randomization)

A randomization schedule will be centrally generated by the protocol statistician. The study will recruit approximately equal numbers of males and females, but formal targets for randomization will not be established. **Table 1** shows the planned vaccination group allocation.

Randomization is stratified by clinical site, with a separate list generated for each site. Blocks will be used within each stratum to maintain balance in assignments over time.

Randomized participants who withdraw before receiving study vaccination will be replaced, with the replacement participant receiving the same assignment.

After the protocol amendment to reduce the total sample size, implemented in version 5.0 of the protocol, a new set of assignments was generated for Groups 3 and 4 based on the updated allocation ratios. Randomization into Groups 1 and 2 was stopped prior to the initial target, to approximately maintain these new group sizes.

4.5. Study Products

4.5.1. Study Products Administered

Study products administered include the IHV01 HIV-1 vaccine, the glycoprotein A244, and the ALFQ adjuvant. Saline will be used as placebo for the study.

4.5.2. Identity of Investigational Product(s)

IHV01, an Institute of Human Virology (IHV) product, consists of the FLSC gp120-CD4 chimera subunit HIV-1 vaccine formulated in Aluminum phosphate adjuvant (Alum). The formulation consists of 0.3 mg/mL of FLSC, 2.4 mg/mL of Alum, 5 mM NaOAc, 40 mg/mL mannitol, pH 6.2.

A244, a Duke University product, consists of the gp120 envelope glycoprotein HIV-1 subtype CRF_01AE A244 derived from the CM244 CRF_01AE. The A244 gp120 envelop has an 11-amino N-terminal deletion, similar to the bivalent AIDVAX® B/E protein used in RV144 ([Alam, 2013](#)), which has been safely administered to over 9,000 participants. The AHFG adjuvant that is mixed with A244 consists of Rehydragel HPA that has been diluted with sterile water and has an aluminum concentration of 5 ± 1 mg/mL.

ALFQ, a US Army product, is a liposomal adjuvant containing a synthetic monophosphoryl lipid A (3D-PHAD®) with the addition of QS-21.

Saline (sodium chloride for injection USP, 0.9%) will serve as a placebo for the trial.

Refer to Section 7.4 of the protocol for additional information.

4.5.3. Selection of Doses in the Study

Participants will receive a one-time injection of either IHV01 and A244/AHFG (n=64) or saline placebo (n=16) at Day 0. Half of the IHV01 and A244/AHFG recipients will receive the full dose (Groups 1 and 3) of each vaccine while half will receive a fractional dose (Groups 2 and 4) of each vaccine, which is one fifth of the full dose. Groups 3 and 4 will also receive ALFQ.

4.5.4. Selection and Timing of Dose for Each Participant

This is a single-dose study, with participants receiving the assigned study product at Day 0.

4.5.5. Blinding

The PI, study staff, and participants will be blinded as to receipt of active vaccines or placebo but will not be blinded to group allocation as it pertains to the inclusion of ALFQ, due to the planned sequential enrollment. Since the vaccines and placebos are not identical in appearance, to preserve blinding the material inside the syringe will be masked by the pharmacist. In addition, the pharmacy staff preparing the vaccine syringes will not be involved in the clinical assessment of participants and will be instructed not to comment on the appearance of experimental agent to study staff. For all participants, the volume of injection will be consistent.

4.5.6. Prior and Concomitant Therapy

Information pertaining to receipt of non-study vaccines, research agents, immunoglobulin preparations, immunosuppressive medication, antiretroviral drugs, and any blood products will be elicited at study visits and recorded in source documents.

To ensure appropriate medical follow-up for study participants, information regarding concomitant medications used in association with an AE will be collected and recorded in the source documents.

Otherwise, no other concomitant medication information will be collected.

4.5.7. Study Product Compliance

Any randomized participants who withdraw before receiving the study vaccination will be summarized in the participant disposition exhibits and reported in a listing. Those participants will be replaced by others determined to be eligible during screening visits.

4.6. Safety Variables

Safety will be assessed both by direct physical examination and by diary cards (see Appendix O of the protocol), which serve as memory tools for better identification of reactions. During visits on Day 0 (pre- and post-vaccination), Day 1, and Day 7, participants will be assessed for symptoms of local (at the injection site) reactogenicity: erythema, induration, pain/tenderness, swelling and limitation of leg movement, and for symptoms of systemic reactogenicity: fever, tiredness, chills, myalgia, arthralgia, headache, nausea, and rash. After review of the diary card and discussion with the participant, the study staff will document any post-vaccination reaction(s) and all related information (severity, frequency, etc.) concerning such a reaction in the participant's clinic source documents. The frequency and incidence of specific post-vaccination reactions and any reaction will be used for analysis.

AEs and SAEs will be recorded at all visits along with timing and possible attribution to Investigational Product. Because this clinical trial involves an adjuvant, AESIs will also be assessed. As with solicited events, the frequency and incidence of specific post-vaccination reactions and any reaction will be used for analysis.

Safety laboratory analyses of complete blood count, liver function tests, urinalysis, and pregnancy test in females will also be performed according to the SOE. In addition to abnormal findings reported as AEs, changes from baseline will be computed.

Vital signs (body temperature, pulse, respiratory rate, and blood pressure) will be measured both pre- and at about 30 minutes post-vaccination.

4.7. Immunogenicity Variables

Vaccine-induced immune responses will be assessed in study participants as detailed in the SOE. Humoral responses will be assessed by HIV-specific binding and neutralizing antibody assays at Days 0, 14, 168, and possibly at Day 336. HIV-specific binding antibody responses in the rectal, semen and cervico-vaginal mucosal compartments will be assessed using non-invasive sampling methods (sponge, cup, and masturbation) at Days 0, 14, and 168. Cell-mediated immune responses will be assessed via PBMCs and by utilizing optional invasive sigmoid and lymph node biopsies that will be performed at Day 14, dependent on sample availability. Results of immunology assessments through invasive collection methods in the mucosal compartments are exploratory and will be mostly descriptive as performed in a limited number of participants.

Measurement of CD4+ and CD8+ T-cell effector function will be evaluated through response by cytokines such as IFN- γ and IL2 at Days 0, 14, 168, and possibly at 336. The CD4+ function will also be assessed by the lymphoproliferation responses as measured by the functional CFSE assay at Days 0 and 14. Innate immunity (e.g., NK cells) will be assessed by quantifying ADCC, ADCP and cytokines produced by NK cells at Days 0, 14 and 168, determining innate cells' phenotype and function using various flow cytometric panels at Days 0, 1, 7, and 14, cytokine array assays to characterize the type of cytokines elicited by this vaccine regimen with or without adjuvants, and other related assays. Granulocytes and neutrophils (NET assay) will also be assessed in whole blood at Days 0, 14, and 168.

B-cell responses will be characterized in blood at Days 0, 7, 14, and 168 and in diverse anatomical compartments (provided by sigmoid and lymph nodes biopsies) in a subset of participants, dependent on sample availability.

Leukapheresis will be performed at Day 14 in a subset of willing participants for in-depth investigations of the T-cell responses.

In the context of unknown immune correlates of protection, additional assessments may be performed as new scientific technologies and assessment tools are made available.

4.8. Genomic Variables

Next-generation sequencing methodologies will explore the innate and early adaptive immune responses to vaccination by screening genomic expression profile in PBMCs. Transcriptome data may be generated using RNASeq to investigate gene transcription profile and signature to vaccine antigens in a subset of participants.

Exploratory genomic and transcriptomic analyses will be described in a separate document.

4.9. Other Variables

Age, gender, gender identity, date of birth, level of education, occupation and baseline medical history of participants will be recorded. Participant disposition variables will include the numbers of participants in each group and overall completing visits and study assessments.

Analyses of next-generation sequencing, RNA sequencing, proteome and microbiome analyses will be conducted separately.

5. GENERAL STATISTICAL CONSIDERATIONS

5.1. General Principles

All continuous variables will be summarized using the following descriptive statistics: n (non-missing sample size), mean, standard deviation, median, maximum and minimum. The frequency and percentages (based on the non-missing sample size) of observed levels will be reported for all categorical measures. In general, all data listings will be sorted by site, vaccination group and participant, and when appropriate by visit number within participant. All summary tables will be structured with a column for each vaccination group in the order presented in the protocol and will be annotated with the total population size relevant to that table/vaccination group, including any missing observations.

5.2. Timing of Analyses

The final study report will be completed when all primary objective data and secondary immunogenicity endpoint data are available. Additional exploratory immunogenicity analyses may be presented in separate reports and/or manuscripts, depending on data availability.

Interim immunogenicity analyses may be performed while the study is ongoing, but the results of any such analyses will not impact the conduct of the trial. Those analyses would follow the principles outlined in this SAP and would align with those conducted as part of the final study report.

5.3. Analysis Populations

A tabular listing of all participants, visits, and observations excluded from the analysis populations will be provided in the final report.

5.3.1. Safety Population

All participants who received the active vaccination or placebo, and for whom any post-dose data is available, will be included in the safety population.

5.3.2. Immunogenicity Population

The immunogenicity population will consist of all eligible participants who received the vaccination or placebo and have at least one measured post dose blood sample collected.

5.4. Covariates and Subgroups

Gender is a key covariate of interest. While the study is not specifically powered to detect gender differences, some safety and immunogenicity analyses will also be described by gender to evaluate potential gender-specific differences.

RV306 vaccination regimen and time from final RV306 study vaccination to RV546 study vaccination will be assessed in exploratory immunogenicity analyses.

5.5. Missing Data

All attempts will be made to collect all data per protocol. No imputation will be performed for missing values. Outliers will not be excluded from the primary analyses but will be discussed in the analysis report. The number of non-missing values in each group will be described for all analyses.

5.6. Interim Analyses and Data Monitoring

While no formal analyses are planned, interim immunogenicity analyses may be performed while the study is ongoing, but the results of any such analyses will not impact the conduct of the trial. These analyses would follow the principles outlined in this SAP and would align with those conducted as part of the final study report. The interim data would be assigned a blinded unique identifier separate from participant ID to ensure maintenance of blinding.

Any analyses conducted prior to the end of the scheduled follow-up visits will not compromise the integrity of the trial in terms of participant retention or safety or immunogenicity endpoint assessments.

5.7. Multicenter Studies

Data will be pooled across both clinical sites. Center effects are not anticipated because the sites are using standardized procedures for vaccination and assessment of solicited and unsolicited adverse events, and the study relies on central laboratories for the assessments of clinical laboratory endpoints and individual immunogenicity endpoints. Baseline characteristics will be presented by site, to assess the balance of any possible confounders between sites.

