5.9. Study Population

A total of 80 healthy, HIV-uninfected participants at a low risk for HIV infection, available for 12 months, who were randomized to receive active vaccine in RV306 and completed all vaccinations will be enrolled. A total of 274/300 (91.3%) active recipients from Groups 2, 3, 4a, and 4b received all vaccinations and completed all study visits in RV306.

Each site will recruit participants who participated in RV306 at their respective sites, however recruitment may also include participants who participated in RV306 at the site in Chiang Mai University if the participant is willing to be enrolled and followed at one of the two Bangkok sites. It is anticipated that up to 110 prior RV306 participants will be screened in order to enroll 80 participants into RV546. As much as possible, an equivalent proportion of male and female participants will be enrolled into each arm of the study.

Study staff and participants will be blinded to vaccine/placebo and full dose/fractional dose assignment. As a byproduct of the sequential enrollment of the vaccine/placebo groups, study staff will not be blinded to a participant's receipt of ALFQ. Groups 1 and 2 (without ALFQ adjuvant) will be enrolled first in a randomized, double-blinded manner. Enrollment into Groups 1 and 2 will begin with no more than two participants per site per week for the first two weeks. Once at least 7-days of safety data is available from the first eight participants enrolled across Groups 1 and 2, the Safety Monitoring Committee (SMC) will review 7-days of safety data from these participants to determine whether enrollment can continue. Enrollment into Groups 1 and 2 will be unrestricted after any safety concerns raised by the SMC are addressed and the Sponsor has given their approval for continuation of enrollment. Enrollment into Groups 3 and 4 will commence after enrollment into Group 1 and Group 2 has been completed, the SMC has reviewed 7-days of safety data from all Group 1 and 2 participants, and the Sponsor gives their approval. Enrollment into Groups 3 and 4 will follow a similar approach with no more than two participants per site per week for the first two weeks, followed by an SMC review of 7-days of safety data from the first eight participants enrolled across both Groups, and Sponsor approval before enrollment can continue unrestricted in Groups 3 and 4. The PI, investigators and study participants will remain blinded to vaccine and placebo allocation.

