5.8. Multiple Comparisons/Multiplicity

For comparisons of safety outcomes, 5%-level two-sided tests will be made. Some of these may be implicit comparisons based on the overlap of group-level confidence intervals (i.e. non-overlapping 95% CIs mean rejecting the null hypothesis of no difference between groups at the 0.05-level).

To compare primary immunogenicity outcomes (antigen-specific plasma IgG binding responses, as measured by log AUC over time) across all groups, 5%-level two-sided tests will be used. When differences are found, pairwise comparisons between vaccination groups will be made using the Bonferroni-Holm step-down procedure [1] and a 5% significance threshold for the adjusted p-values; if no difference is found across all groups, no pairwise comparisons will be made. Collapsed comparisons will be considered separately and will be made with 2.5%-level two-sided tests, even when no pairwise differences are observed.

Further exploratory comparisons for immunogenicity endpoints across all groups will be adjusted for multiplicity by a Bonferroni adjustment: multiplying p-values by the number of assays in the same set (e.g. across antigens for a given antibody test; see Section 3.2.2 for sets of assays). Then a similar process as above will be followed, with pairwise comparisons following a significant overall test and Bonferroni-Holm step-down procedure (with a 5% significance level) to account for the multiple pairwise tests.

These adjustments are intended to improve control of the type-I error across comparisons for the same outcome measure and time point (e.g. Geometric Mean Titers (GMTs) for gp120A244 plasma IgG binding at Day 14) rather than across outcome measures and/or time. This level of type-I error control will still allow for exploratory findings that would be assessed further in future studies.

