7.1. Primary Safety Analysis

7.1.1. Unsolicited Adverse Events

Unsolicited AEs will be listed and summarized by MedDRA system order class (SOC) and preferred term (PT) for each vaccination group. These will be described overall and within 28 days post-vaccination. A participant will be counted only once per PT per reporting period. SAEs, unexpected AEs, and AESIs will be summarized and listed. The number and percentage of participants reporting each PT, along with the associated 95% exact Clopper-Pearson CI for the underlying probability of the event, will be presented.

The likelihood of reporting AEs, SAEs, and AESIs will be compared between collapsed groups (Groups 1+2 vs. Groups 3+4 to assess ALFQ safety, Groups 1+3 vs. Groups 2+4 to assess vaccine dose) via exact binomial tests. If computational challenges arise, Chi-squared tests may be used instead. Calculated confidence intervals will be used to compare pairs of individual vaccination groups, instead of formal hypothesis testing; when CIs for the same event in two groups do not overlap, this corresponds to a p-value of less than 0.05 for the analogous exact binomial test.

Unsolicited AEs will also be tabulated by investigator-determined relationship to investigational product and severity for each vaccination group.

Incident HIV infections, as diagnosed by the algorithm in Section 11.1.4.4 of the protocol, will be presented in a listing.

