8. IMMUNOGENICITY EVALUATION

8.1. Primary Immunogenicity Analysis

The primary immunogenicity endpoint is the magnitude of plasma IgG (antigen-specific) responses as measured by the endpoint titer, the same variable assessed in RV306. GMTs will be calculated for each group at each visit and the per-participant peak across all visits, along with 95% CIs (exponentiating the CI limits for the log GMT based on the normal distribution). Hypothesis testing is planned for targeted time points; this will be performed in order to aid in interpretation by helping to determine immune responses for potential further examination in future studies. First, group GMTs will be compared across all vaccination groups via ANOVA (null hypothesis that all groups share the same GMT) at the 5%-level, and if that is found to be significant, pairwise comparisons via 2-sided t-tests and the Bonferroni-Holm step-down procedure will be made and a 1% significance threshold will be applied. The two collapsed comparisons will be via 2-sided t-tests of log-GMTs at the $\alpha=0.025$ -level. If the data appear especially non-normal, nonparametric testing will be considered instead.

The reverse cumulative distribution (RCD) of titers (with endpoint titer on the x-axis and the proportion of participants with at least that titer on the y-axis) at each visit will be shown by vaccination group, separately for each antigen.

Seroconversion or seropositivity post-vaccination will be defined based on criteria given by the performing lab, and the number and percent of participants in each group achieving seroconversion/seropositivity at each visit will be presented along with the associated exact 95% Clopper-Pearson CI. The same group comparisons will be performed, via exact binomial tests and the same handling of significance and multiplicity.

Immune response over time (durability) will be assessed by the positive incremental area under the curve (AUC) based on a graph with log endpoint titer on the y-axis and visit day on the x-axis. For comparability between participants with different numbers of samples (visits) available, these values will be scaled by the week of the last available sample. If no sample is available for visits other than the first and last, no explicit imputation will be done, and the AUC will be calculated based on available samples. Log AUC will be analyzed similarly to the visit-by-visit titers.

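### Site is a stratification factor in the randomisation but appears in no immunogenicity test or model; this costs power where site is balanced and leaves comparisons across enrolment phases open to a shift in site mix.

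*SAP*

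**What the plan says.** SAP 4.4.2 on allocation: "Randomization is stratified by clinical site, with a separate list generated for each site". It continues: "Blocks will be used within each stratum to maintain balance in assignments over time". Block size is not stated. The same section says that new assignments were generated for Groups 3 and 4 after the sample-size amendment and that randomisation into Groups 1 and 2 stopped short of its initial target. SAP 4.1 has Groups 1 and 2 accrue first and Groups 3 and 4 afterwards, at 2:2:1 full to fractional to placebo in each phase.

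SAP 5.7 on analysis: "Data will be pooled across both clinical sites. Center effects are not anticipated because the sites are using standardized procedures". It also cites central laboratories, and it plans baseline tables by site.

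The tests that follow contain no site term:
- SAP 8.1, overall test: "First, group GMTs will be compared across all vaccination groups via ANOVA".
- SAP 5.8, dose and ALFQ contrasts: "Collapsed comparisons will be considered separately and will be made with 2.5%-level two-sided tests". SAP 8.1 specifies these as t-tests.
- SAP 7.1.1, safety, for the same collapsed groups: "via exact binomial tests. If computational challenges arise, Chi-squared tests may be used instead".
- SAP 8.2: the GEE has dose, adjuvant, study day and their interactions. The exploratory regression has vaccination group, age, sex, RV306 group and time since the last RV306 dose.

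Protocol 5.9 on who is enrolled: "Each site will recruit participants who participated in RV306 at their respective sites". It adds that former Chiang Mai participants may join either Bangkok site.

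**The concern.** Standardised procedures and central laboratories limit differences in how responses are measured. They do not make the two sites' participants alike. Each site draws mainly on its own RV306 cohort, so age, sex, RV306 arm and time since the last boost could differ by site. The SAP treats RV306 regimen and interval as worth examining (5.4, 8.2), but no step in the immunogenicity tests follows from the planned by-site tables.

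If site predicts titer, leaving it out has one of two effects:
- **Site balanced between the arms.** The between-site variance stays in the error term although it does not affect the difference in means. The standard error is too large, the test runs below its nominal level, and power falls.
- **Site not balanced between the arms.** Part of the site difference enters the estimated effect, which can push type I error above nominal.

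The dose contrast is of the first kind, because both doses are randomised concurrently within site in each phase. ALFQ v no ALFQ, which Protocol 12.2.3 names as a key safety comparison and SAP 8.1 tests for immunogenicity, is of the second kind. So are the cross-phase pairwise tests and the five-group ANOVA. Stratification acts only within a phase, and no text requires the same site mix in both.

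**Working it through.** **1. The plan's own figures.** SAP Table 4 (Protocol Table 8) gives detectable differences at 80% power and two-sided alpha 0.05. The exact two-sample t-test (noncentral t, n1+n2−2 df) gives 0.793, 0.711 and 1.024 SD for 64 v 16, 32 v 32 and 16 v 16, against 0.79, 0.71 and 1.02 stated. They reproduce. SAP 5.8 and 8.1 test the collapsed contrasts at 0.025, where the 32 v 32 figure is 0.787, so 0.79 SD is used below as the effect with 80% power.

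**2. Assumption.** The documents give no difference between sites. Let d be that difference in within-site SD, taken from 0 to 1.0, with equal site sizes.

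**3. Site balanced: dose contrast, 32 v 32, alpha 0.025.** With within-site SD 1, the true standard error of the difference is √(2/32) = 0.25, so the signal is 0.79/0.25 = 3.16. The pooled test estimates the SD as about √(1 + d²/4). Its critical value of 2.297 (62 df) becomes in effect 2.297 × √(1 + d²/4), and power is about Φ(3.16 − that value):
- d = 0: 2.297, Φ(0.863) = 0.81
- d = 0.5: 2.297 × 1.031 = 2.368, Φ(0.792) = 0.79
- d = 1.0: 2.297 × 1.118 = 2.568, Φ(0.592) = 0.72

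Simulation agrees:

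| d (SD) | Power, pooled | Power, site term | Type I, pooled | Type I, site term |
|---|---|---|---|---|
| 0 | 80.4% | 80.3% | 2.5% | 2.5% |
| 0.25 | 79.8% | about 80% | 2.4% | 2.5% |
| 0.5 | 78.2% | 80.3% | 2.1% | 2.5% |
| 1.0 | 72.2% | 80.4% | 1.2% | 2.5% |

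The loss is under 1 point at 0.25 SD, about 2 at 0.5 SD and about 8 at 1.0 SD.

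**4. Site not balanced: ALFQ v no ALFQ, 32 v 32, alpha 0.025.** Suppose one site supplies 12 of 32 active participants in one phase and 20 of 32 in the other. The bias is d × (20 − 12)/32 = 0.25d, which is d standard errors (0.25d/0.25). The pooled SD is about √(1 + d² × 12/32 × 20/32) = √(1 + 0.234d²). With no true effect:
- d = 0.5: critical value 2.297 × 1.029 = 2.363; Φ(−1.863) + Φ(−2.863) = 3.3%
- d = 1.0: critical value 2.297 × 1.111 = 2.552; Φ(−1.552) + Φ(−3.552) = 6.0%

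This hand calculation treats the SD as known and so runs slightly low. Simulation gives about 3.7% and 6.6%. Other assumed mixes:
- 14 v 18: between 2.3% and 2.5%, so no inflation
- 10 v 22: about 6% (0.5 SD) and 16% (1.0 SD)

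With a site term, type I error stays between 2.4% and 2.6% in all these settings.

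**The case against.** **The endpoint is secondary and the trial exploratory.** The primary objective is safety, the protocol calls the study descriptive, and SAP 8.1 presents testing as an aid to interpretation. This stands and limits the weight of the point.

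**The site difference is hypothetical.** Both sites are in Bangkok, draw on one earlier trial under common criteria and use central laboratories. Below about 0.5 SD the loss is trivial. The 8-point loss needs a full 1.0 SD difference and an even split between sites; at 75:25 pooled power is 74.2%. This also stands.

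**The sizing SD may already include site variation.** RV306 was itself multi-site. If the planning SD is a total SD, which the documents do not say, a 0.79 total-SD effect keeps pooled power at 80.8% (0.5 SD) or 82.4% (1.0 SD). Omitting site then forgoes a gain and does not erode planned power. Either way the site-adjusted analysis is the more powerful one when the sites differ.

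**Adjustment is partly planned.** The SAP 8.2 regression covers age, sex, RV306 group and interval, the likely routes to a site difference. But it is exploratory and does not supply the tests in SAP 8.1.

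**Balance by site rests on the SAP.** Protocol 7.3.1 describes contiguous slots from a random list assigned to each clinic and mentions no blocks. Incomplete blocks would also leave some imbalance. If balance is weaker than SAP 4.4.2 implies, the case for a site term is not reduced.

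A reader might infer that every planned test is conservative. The documents do not support that: the sequential phases and the separate list for Groups 3 and 4 leave site mix free to differ between ALFQ and no ALFQ.

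**Conclusion.** The concern holds with limits. Randomisation uses site and the immunogenicity analysis ignores it, for a reason that covers measurement only. For the dose contrast and comparisons within a phase, the pooled test is conservative, with a loss of about 2 points of power at a 0.5 SD site difference and about 8 at 1.0 SD. For ALFQ v no ALFQ, cross-phase pairwise tests and the five-group ANOVA, the direction is not assured: type I error can exceed nominal if the site mix shifts materially between phases.

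These sizes rest on assumed site differences and site mixes. Nothing in the documents shows that the sites differ or that the mix did shift, so it cannot be concluded that the planned tests are invalid. Nor can the power figures be carried over to the safety tests, which are exact tests of sparse binary events and were not evaluated here. The change is worth making because it protects power in one case and type I error in the other, at almost no cost.

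**What to change.** - **SAP 5.7 and 8.1.** Analyse log titer and log AUC by a linear model with vaccination group and site. Take the overall test, the Holm-adjusted pairwise tests and the two collapsed contrasts from that model, at the significance levels already planned.
- **SAP 8.2.** Add site to the regression and to the GEE.
- **SAP 5.7.** Replace the statement that center effects are not expected with one saying that site is included because it is a stratification factor.
- **Safety (SAP 7.1.1), optional.** A site-stratified exact Cochran-Mantel-Haenszel result may be shown as a supportive sensitivity analysis. State that the unstratified exact test governs.
- **Interpretation of ALFQ v no ALFQ.** Report the site mix by phase, and say that a site term does not remove calendar-time differences between phases enrolled in sequence.

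The cost is SAP wording and one degree of freedom, with no measurable loss of power if the sites do not differ (80.3% with the site term against 80.4% without, within simulation error). Trial conduct is unaffected.
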